6.3 Follow-up

Patients will be followed either with clinic visits or phone interviews yearly for two years.

Patients removed from treatment for unacceptable adverse event(s) will be followed clinically until

resolution or stabilization of the adverse event, and then via clinic visits or phone interviews yearly for two years.

The following information will be collected:

- Date of follow up
- Is patient dead or alive?
- If dead, document exact date of death.
- Further treatment(s), if any
- Document date of disease progression
- Long-term myelosuppression, myelodysplasia, and occurrence of secondary malignancies.

6.4 Study Calendar

Please refer to **Appendix D**.

7.0 Measurement of Effect

7.1 Antitumor Effect- Solid Tumors

Response and progression will be evaluated in this study using the international criteria proposed by the Response Evaluation Criteria in Solid Tumors (RECIST) version 1.1 [47]. Changes in only the largest diameter (unidimensional measurement) of the tumor lesions and the shortest diameter in the case of malignant lymph nodes are used in the RECIST version 1.1 criteria.

7.1.1 Definitions

Evaluable for toxicity: All patients will be evaluable for toxicity from the time of their first treatment with $^{177}\text{Lu-DOTA}^0\text{-Tyr}^3\text{-Octreotate}$ and nivolumab.

Evaluable for objective response: Only those patients who have received at least one cycle of therapy, and have had their disease re-evaluated will be considered evaluable for response. These patients will have their response classified according to the definitions stated below. (Note: Patients who exhibit objective disease progression prior to the end of cycle 1 will also be considered evaluable.)

Evaluable Non-Target Disease Response: Patients who have lesions present at baseline that are evaluable but do not meet the definitions of measurable disease, have received at least one cycle of therapy, and have had their disease reevaluated will be considered evaluable for non-target disease. The response assessment is based on the presence, absence, or unequivocal progression of the lesions.

7.1.2 Disease Parameters

Measurable disease: Measurable lesions are defined as those that can be accurately measured in at least one dimension (longest diameter to be recorded) as ≥ 20 mm by chest x-ray, as ≥ 10 mm with CT scan, or 10 mm with calipers by clinical exam. All tumor measurements must be recorded in millimeters (or decimal fractions of centimeters).

Note: Tumor lesions that are located in a previously irradiated area might or might not be considered measurable at the discretion of the PI.

Malignant lymph nodes: To be considered pathologically enlarged and measurable, a lymph node must be ≥ 15 mm in short axis when assessed by CT scan (CT scan slice thickness recommended to be no greater than 5 mm). At baseline and in follow-up, only the short axis will be measured and followed.

Non-measurable disease: All other lesions (or sites of disease), including small lesions (longest diameter < 10 mm or pathological lymph nodes with ≥ 10 to < 15 mm short axis), are considered non-measurable disease. Bone lesions, leptomeningeal disease, ascites, pleural/pericardial effusions, lymphangitis cutis/pulmonis, inflammatory breast disease, abdominal masses (not followed by CT or MRI), and cystic lesions are all non-measurable.

Note: Cystic lesions that meet the criteria for radiographically defined simple cysts should not be considered as malignant lesions (neither measurable nor nonmeasurable) since they are, by definition, simple cysts.

'Cystic lesions' thought to represent cystic metastases can be considered as measurable lesions, if they meet the definition of measurability described above. However, if non-cystic lesions are present in the same patient, these are preferred for selection as target lesions.

Target lesions: All measurable lesions up to a maximum of 2 lesions per organ and 5 lesions in total, representative of all involved organs, should be identified as **target lesions** and recorded and measured at baseline. Target lesions should be selected on the basis of their size (lesions with the longest diameter), be representative of all involved organs, and their suitability for accurate repeated measurements (either by imaging techniques or clinically). A sum of the diameters (longest for non-nodal lesions, short axis for nodal lesions) for all target lesions will be calculated and reported as the baseline sum diameters. If lymph nodes are to be included in the sum, then only the short axis is added into the sum. The baseline sum diameters will be used as reference to further characterize any objective tumor regression in the measurable dimension of the disease.

Non-target lesions. All other lesions (or sites of disease) including any measurable lesions over and above the 6 target lesions should be identified as **non-target lesions** and should also be recorded at baseline. Measurements of these lesions are not required, but the presence or absence of each should be noted throughout follow-up.

7.1.3 Methods for Evaluation of Measurable Disease

All measurements should be taken and recorded in metric notation using a ruler or calipers. All baseline evaluations should be performed as closely as possible to the beginning of treatment and never more than 28 days before the beginning of the treatment.

The same method of assessment and the same technique should be used to characterize each identified and reported lesion at baseline and during follow-up. Imaging-based evaluation is preferred to evaluation by clinical examination unless the lesion(s) being followed cannot be imaged but are assessable by clinical exam.

Clinical lesions: Clinical lesions will only be considered measurable when they are superficial (e.g., skin nodules and palpable lymph nodes) and ≥ 10 mm diameter as assessed using calipers (e.g., skin nodules). In the case of skin lesions, documentation by color photography, including a ruler to estimate the size of the lesion, is recommended.

Conventional CT and MRI: CT and MRI - CT and MRI are the best currently available and reproducible methods to measure target lesions selected for response assessment. For this study helical multidetector CT will be performed with cuts of 5 mm in slice thickness for chest, abdomen and pelvis lesions and 2-3 mm thickness for head and neck lesions. For consistency, it is recommended that investigators use the same imaging modality for follow-up of tumors for a given patient.

Cytology, Histology: These techniques can be used to differentiate between partial responses (PR) and complete responses (CR) in rare cases.

The cytological confirmation of the neoplastic origin of any effusion that appears or worsens during treatment when the measurable tumor has met criteria for response or stable disease is mandatory to differentiate between response or stable disease (an effusion may be a side effect of the treatment) and progressive disease.

FDG-PET: New lesions on the basis of FDG-PET imaging can be identified according to the following algorithm. Negative FDG-PET at baseline, with a positive FDG-PET at follow-up may be a sign of progressive disease. If the positive FDG-PET at follow-up corresponds to a new site of disease confirmed by CT, this is progressive disease (PD). If the positive FDG-PET at follow-up is not confirmed as a new site of disease on CT, additional follow-up CT scans are needed to determine if there is truly progression occurring at that site. If so, the date of PD will be the date of the initial abnormal FDG-PET scan. If the positive FDG-PET at follow-up corresponds to a pre-existing site of disease on CT that is not progressing on the basis of the anatomic images, this is not PD.

Note: A positive FDG-PET scan lesion means one which is FDG avid with an uptake greater than twice that of the surrounding tissue on the attenuation corrected image.

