5.1.2 Phase II

The phase II portion will consist of patients with ES-SCLC who completed platinum based standard first-line chemotherapy (e.g. 4-6 cycles of platinum plus etoposide or irinotecan) without disease progression (responders plus stable disease) at the time of initiation of the combination therapy with $^{177}\text{Lu-DOTA}^0\text{-Tyr}^3\text{-Octreotate}$ and nivolumab. Eligible patients will then be randomly allocated in two arms: one will be treated with the combination of $^{177}\text{Lu-DOTA}^0\text{-Tyr}^3\text{-}$

Octreotate and nivolumab, and the other arm will continue be followed (observation) after completion the standard chemotherapy treatment.

Randomization:

Patients who do not receive radiotherapy after chemotherapy

- The randomization must occur within 6 weeks of the last chemotherapy cycle.
- The study treatment must start within 2 weeks from randomization, but no less than 2 weeks from last dose of chemotherapy.

Patients who receive radiotherapy (including prophylactic cranial radiation and/or thoracic radiation) after chemotherapy

- Randomization must occur at least 8 weeks after completion of radiation therapy but within 12 weeks after completion of radiation therapy.

Randomization process:

- OnCore will be used as statistical center and the randomization algorithm will be developed by the study biostatistician.
- The project management department will be the first point of contact for assessment through email.

Courses are defined as 56 days of dosing. Nivolumab will be given until progressive disease, patient withdrawal, or toxicities. For patients randomized to the observation group, cross-over at the time of disease progression will be allowed, since the primary endpoint is PFS and not OS.

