7.1.4 Response Criteria

7.1.4.1 Evaluation of Target Lesions

Response and progression will be evaluated in this study using the international criteria proposed by the Response Evaluation Criteria in Solid Tumors (RECIST) version 1.1.

Complete Response (CR): Disappearance of all target lesions. There can be no appearance of new lesions. Any pathological lymph nodes must have reduction in short axis to < 10 mm.

Partial Response (PR): At least a 30% decrease in the sum of target lesions, taking as reference the baseline sum diameters. There can be no appearance of new lesions.

Progressive Disease (PD): At least a 20% increase in the sum of the diameters of target lesions, taking as reference the smallest sum on study (this includes the baseline sum if that is the smallest on study). The appearance of one or more new lesions is also considered progression).

Stable Disease (SD): Neither sufficient shrinkage to qualify for PR nor sufficient increase to qualify for PD, taking as reference the smallest sum diameters while on study.

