7.1.4.2 Evaluation of Non-Target Lesions

Complete Response (CR): Disappearance of all non-target lesions and normalization of tumor marker level. All lymph nodes must be non-pathological in size (<10 mm short axis).

Non-CR/Non-PD: Persistence of one or more non-target lesion(s) and/or maintenance of tumor marker level above the normal limits.

Progressive Disease (PD): Appearance of one or more new lesions and/or unequivocal progression of existing non-target lesions. Unequivocal progression should not normally trump target lesion status. It must be representative of overall disease status change, not a single lesion increase.

Although a clear progression of “non-target” lesions only is exceptional, the opinion of the treating physician should prevail in such circumstances, and the progression status should be confirmed at a later time by the review panel (or Principal Investigator).

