7.1.4.3 Evaluation of Best Overall Response

The best overall response is the best response recorded from the start of the treatment until disease progression/recurrence (taking as reference for progressive disease the smallest measurements recorded since the treatment started). The patient's best response assignment will depend on the achievement of both measurement and confirmation criteria.

Table 7. Evaluation of patients with measureable disease.

Target Lesions	Non-Target Lesions	New Lesions*	Overall Response
CR	CR	No	CR
CR	Non-CR/Non-PD	No	PR
CR	Not evaluated	No	PR
PR	Non-CR/Non-PD/not evaluated	No	PR
SD	Non-CR/Non-PD/not evaluated	No	SD
PD	Any	Yes or No	PD
Any	PD**	Yes or No	PD
Any	Any	Yes	PD

* See RECIST 1.1 manuscript for further details on what is evidence of a new lesion.

****** In exceptional circumstances, unequivocal progression in non-target lesions may be accepted as disease progression.

Note: Patients with a global deterioration of health status requiring discontinuation of treatment without objective evidence of disease progression at that time should be reported as “symptomatic deterioration”. Every effort should be made to document the objective progression even after discontinuation of treatment.

Table 8. Evaluation of patients with non-measurable disease

Non-Target Lesions	New Lesions	Overall Response
CR	No	CR
Non-CR/non-PD	No	Non-CR/non-PD*
Not all evaluated	No	Not evaluated
Unequivocal PD	Yes or No	PD
Any	Yes	PD
* ‘Non-CR/non-PD’ is preferred over ‘stable disease’ for non-target disease since SD is increasingly used as an endpoint for assessment of efficacy in some trials so to assign this category when no lesions can be measured is not advised.		

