11.0 STATISTICAL CONSIDERATIONS

11.1 Study Design

This is a phase I/II clinical trial of $^{177}\text{Lu-DOTA}^0\text{-Tyr}^3\text{-Octreotate}$ and nivolumab, in patients with ES-SCLC. The primary endpoint of the phase I portion is to determine the recommended phase II doses of $^{177}\text{Lu-DOTA}^0\text{-Tyr}^3\text{-Octreotate}$ when given in combination with nivolumab. Patients with relapsed or refractory ES-SCLC and patients with advanced or inoperable grade I-II pulmonary NETs are also eligible for the phase I portion. For all patients participating in this phase I/II study, a positive SRI (Somatostatin Receptor Imaging) scan showing overexpression of SSTR2 will be mandatory for inclusion (NETSPOT®). The phase II portion will consist of patients with ES-SCLC that completed standard first-line chemotherapy with a platinum-based regimen, without disease progression (responders plus stable disease) at the time of initiation the combination therapy with $^{177}\text{Lu-DOTA}^0\text{-Tyr}^3\text{-Octreotate}$ and nivolumab. Patients will be randomly allocated in two arms: one will be treated with the combination of $^{177}\text{Lu-DOTA}^0\text{-Tyr}^3\text{-Octreotate}$ and nivolumab, and the other arm will continue be followed (observation) after completion the standard chemotherapy treatment. Cross-over will be permitted at the time of disease progression.

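### The effusion cytology rule is worded for patients on treatment, so read literally it leaves the observation arm without the check on progression that the combination arm has

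*Combined protocol and SAP*

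**What the plan says.** Section 7.1.3 (cytology and histology) states that confirming by cytology the malignant origin of "any effusion that appears or worsens during treatment when the measurable tumor has met criteria for response or stable disease is mandatory". The purpose is to separate response or stable disease from progression, and the reason given is that "an effusion may be a side effect of the treatment) and progressive disease".

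The other provisions that bear on an effusion are these:

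- Section 7.1.2 lists as non-measurable disease "Bone lesions, leptomeningeal disease, ascites, pleural/pericardial effusions", among others.
- Section 7.1.4.1 adds to the target-lesion criterion: "The appearance of one or more new lesions is also considered progression".
- Section 7.1.4.2 defines non-target progression as "Appearance of one or more new lesions and/or unequivocal progression of existing non-target lesions". Neither this section nor 7.1.4.1 sets a cytology condition.
- Section 11.1 describes the control group: "the other arm will continue be followed (observation) after completion the standard chemotherapy treatment". Section 5.1.2 adds: "For patients randomized to the observation group, cross-over at the time of disease progression will be allowed".
- Sections 7.1.6 and 11.3 count PFS from randomization in both arms. The précis calls the trial open-label.

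**The concern.** Both the trigger of the cytology rule and its reason presuppose a patient on drug. An observation patient has no such period before the PFS event, because the combination is available only after progression. The same finding, an effusion with target lesions in response or stable, could then be progression at once in one arm and need positive cytology in the other.

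This touches the primary endpoint of a small randomized comparison. No blinded independent review of progression is described. Declaring progression in the observation arm also opens access to the combination, an incentive in the same direction. Extra or earlier control events, or later experimental ones, would all move the PFS hazard ratio towards the combination.

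**Working it through.** **1. The provisions side by side.** Take a patient whose measurable tumor is in response or stable disease and who has a new or worse effusion.

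| | Combination, on drug | Combination, drug stopped | Observation |
|---|---|---|---|
| Section 7.1.3 cytology rule, read literally | applies | does not apply | does not apply |
| New effusion taken as a new lesion (7.1.4.1, 7.1.4.2, Table 7) | progression only if cytology is positive | can be progression without cytology | can be progression without cytology |
| Worse existing effusion (7.1.4.2) | progression only if cytology is positive | progression if unequivocal and representative of overall disease | same as the column to the left |

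No other section gives an effusion rule for the last two columns. The middle column narrows the difference between arms but does not reverse it.

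**2. The plan's own design figures.** Inputs from section 11.2: medians of 2 and 5 months, two-sided 0.05, 80% power, 40 events, 44 patients, 15% dropout. The allocation ratio is not stated; 1:1 is assumed.

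- Hazard ratio: 2/5 = 0.40, as stated.
- Schoenfeld events: 4 × (1.960 + 0.842)² / (ln 0.40)² = 37.4, so 38. Freedman's formula gives 43. The stated 40 lies between.
- Power with 40 events: Φ(√(40/4) × 0.916 − 1.960) = 82.6%.
- Recruitment: 44/(1 − 0.15) = 51.8, so 52, as stated.

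These figures are not in dispute.

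**3. Illustration of direction and scale.** The documents give no effusion rate, so the input here is an assumption. Suppose effusions counted without cytology add a fraction x to the control-arm hazard only. With no true effect, the apparent hazard ratio is 1/(1 + x). The chance of a significant result for the combination is Φ(√10 × ln(1 + x) − 1.960), against a nominal 2.5%.

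| x | Apparent HR, true HR 1 | Chance of a false win | Apparent HR, true HR 0.40 |
|---|---|---|---|
| 5% | 0.95 | 3.6% | 0.38 |
| 10% | 0.91 | 4.9% | 0.36 |
| 20% | 0.83 | 8.3% | 0.33 |
| 30% | 0.77 | 12.9% | 0.31 |

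**4. A second mechanism: earlier dating.** Suppose instead that the same progressions occur but some in the observation arm are called one scan earlier. Scans are 8 weeks apart (section 6.2). The assumed control median of 2 months is 2 × 52/12 = 8.7 weeks, so one scan interval is 8/8.7, or about 92% of that median. Simulations with no true effect, 40 events and an assumed 2-month median, moving 30% of observation-arm detections one scan earlier, gave mean hazard ratios from 0.91 to 0.83 depending on modelling choices. Moving 10% gave 0.97 to 0.95.

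The two mechanisms agree on direction. Their spread shows that size depends on the model and on an effusion share that the documents do not supply.

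**The case against.** The strongest reply is that section 7 often uses treatment to mean the study. Section 7.1.3 sets the baseline window by the start of treatment. Section 7.1.4.3 counts best response from the same point. Section 7.1.5 measures stable disease from randomization but takes its reference from the start of treatment. Read strictly everywhere, observation patients would have no baseline window or nadir. On that view the effusion rule already covers both arms, and nothing exempts observation patients from cytology. This stands as a possible reading, which is why the point concerns scope and uneven application. It does not settle the matter, because the side-effect reason fits only treated patients.

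Second, section 7.1.4.2 restrains non-target progression in both arms. It should not ordinarily override the target-lesion result and must reflect the disease as a whole. Progression in non-target lesions alone should be confirmed later by a review panel or the principal investigator. Section 7.1.2 does not make every new effusion a malignant new lesion, and Table 7 refers elsewhere for what counts as one. These points stand and shrink the asymmetry for worsening effusions. They say nothing specific about a new effusion, and they do not require cytology.

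Third, the affected group is narrow: target disease in response or stable, effusion as the only sign, progression called under observation, and the matching combination-arm effusion unsampled or negative. The illustrations let no combination-arm effusion be confirmed, so they lean high. That also stands.

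A reader might infer a second one-arm rule from the note in section 7.1.4.3 on "Patients with a global deterioration of health status requiring discontinuation of treatment without objective evidence of disease progression". The documents do not support that as a PFS bias. The label is reserved for patients without objective progression, and sections 7.1.6 and 11.3 count only progression or death.

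**Conclusion.** The point holds as a gap in wording. Followed literally, the plan has one effusion rule for combination patients on drug and another for everyone else. Followed loosely, it may have different rules at different sites. Any bias favours the combination on the primary endpoint.

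The size is unknown. The hazard ratios and false-win rates above rest on assumed effusion shares, 1:1 allocation and control-only misclassification. A reader might take them to mean that the trial's type I error is inflated by a known amount, or that the plan deliberately sets a lower bar for progression under observation. The documents support neither: they give no effusion rate and nowhere say that cytology is unnecessary under observation.

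Severity is minor to moderate. The sample size and event target are unaffected.

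**What to change.** In section 7.1.3:

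1. Replace the limitation to the treatment period with *after randomization, in either arm*, and keep the condition that the measurable tumor is in response or stable disease.
2. State that, for PFS, such an effusion without positive cytology is not by itself progression in either arm. This makes cytology a condition for counting the event, so the endpoint adds no sampling. Whether an effusion is sampled for clinical reasons is outside this point.
3. State one dating rule, the same in both arms, for an effusion that is confirmed later: either the date it first appeared or worsened, or the date of confirmation.

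The cost is a few sentences and no extra patients. The downside is that a few observation-arm progressions will be dated later. Sampling could still differ between arms in an open-label trial, so the rule becomes equal in the text but not necessarily in practice. The change should be made before progression events are classified, because reclassifying them afterwards with the arms known would be hard to defend.
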